3 STUDY DESIGN

LACI-2 will be an investigator-led, Phase IIb preparatory to Phase III, prospective, randomised, 2x2 partial factorial, open label, blinded outcome trial performed in multiple hospital-based centres. The schematic in Figure 2 describes the study design. This Phase will test trial procedures and feasibility, tolerability of drug, provide safety and intermediary outcome endpoints and clinical and cognitive endpoints to power a main Phase III trial which will follow seamlessly from LACI-2 with additional funding. Brain imaging with MRI is to be used in preference to CT for diagnosis of the index stroke wherever possible, but CT is allowed.

Patients who have all of the following:

- 1) suffered a minor stroke with clinical features compatible with a lacunar stroke syndrome (designated as the 'index stroke');
- 2) on contemporaneous brain imaging have either
 - a) on MR imaging, a recent, relevant (in time and location) acute lacunar infarct on diffusion MR imaging, or
 - b) if no visible acute lacunar infarct on diffusion MR imaging then there may be a recent-appearing relevant (in time and location) acute lacunar infarct on FLAIR, T2, or T1, and
 - c) there will be no competing pathology as a cause for stroke (e.g. no acute cortical infarct on diffusion MR imaging or recent-appearing cortical infarct on FLAIR, T2, T1), no intra-cerebral haemorrhage, no stroke mimic such as tumour, or subdural haematoma);
 - d) where CT brain imaging is used soon after stroke instead of MR, a recent relevant (in time and location) small subcortical infarct (e.g. that was not present on CT prior to the stroke, or that becomes visible on a follow-up scan, if available) and no evidence of alternative causes of the stroke symptoms as in 2c above.
- 3) capacity to give consent; and
- 4) meet inclusion/exclusion criteria below (4.2),

will be randomised to start one of four treatments; isosorbide mononitrate only; cilostazol only; both isosorbide mononitrate and cilostazol; or neither isosorbide mononitrate nor cilostazol.

Patients with contraindications to cilostazol can be randomised to isosorbide mononitrate versus no isosorbide mononitrate arms only; patients with contraindications to isosorbide mononitrate can be randomised to cilostazol versus no cilostazol arms only. The partial factorial design allows testing of both drugs when given alone and together.

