4.2 INCLUSION CRITERIA

- Clinical lacunar stroke syndrome.
- Brain scanning* with MR including diffusion imaging wherever possible, and obtained soon after the presentation with stroke, shows either:
 - a recent, relevant (in time and location) acute lacunar infarct on diffusion MR imaging¹,
 - or, if no visible acute lacunar infarct on diffusion MR imaging² then there is no competing pathology as a cause for stroke (e.g. no acute cortical infarct, no acute intra-cerebral haemorrhage, no stroke mimic such as tumour, subdural haematoma);
 - or, if only a CT brain scan is available² as in section 3 above, then there is a small relevant (in age and location) subcortical infarct, or if no infarct then there is no competing pathology as a cause for stroke (e.g. no acute cortical infarct, no acute intra-cerebral haemorrhage, no stroke mimic such as tumour, subdural haematoma).

¹Note that if there is no acute lacunar infarct on MR diffusion imaging but there is a recent-appearing lacunar infarct on FLAIR, T2, or T1 (i.e. no cavitation or ex-vacuo effect; may be slightly swollen, ill-defined edges; or scan in the few weeks before the stroke does not show a lesion but there is an acute lacunar infarct on MR T2, FLAIR, T1 scanning after the stroke in an appropriate area of the brain for symptoms), then the T2, FLAIR, T1 lesion may be counted as the acute lacunar infarct in the absence of a diffusion lesion. Similarly, on CT² a recent relevant small subcortical infarct would not show cavitation or shrinkage/ex vacuo effect.

²Note that about a third of patients with a clinically definite lacunar syndrome do not have a corresponding recent infarct visible on MRI but should still be classed as 'lacunar stroke' if no other explanation can be found for the symptoms. The presence of a recent cortical infarct on FLAIR, T2, T1, the recent timing being indicated by the characteristics above, would count as a competing pathology.

Note that the complete absence of any abnormality on MR or CT brain imaging (no acute subcortical infarct or pre-existing SVD such as white matter hyperintensities, lacunes, etc.) while occasionally seen in lacunar stroke is unusual and should question the diagnosis of lacunar ischaemic stroke.

- Age > 30 years
- Independent in activities of daily living (modified Rankin ≤ 2)
- Capacity to give consent themselves

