Functional outcome: modified Rankin Scale to assess dependency at 6 and 12 months. If participants are unable to be contacted, the central assessor will obtain the most recent modified Rankin Score from the local staff (if available).

Cognitive outcomes: Telephone MOCA, Telephone Interview for Cognitive Status (TICS), mobility and physical functioning sections of the Stroke Impact Scale and the ZUNG will be collected remotely at six and 12 months by the central trial team. TRAILS B will be repeated when attending for 1 year MR in Centres that are able to do this. TICS will be collected for consistency with prior and ongoing trials (ENOS, TARDIS, RIGHT 2, TICH) and good comparability.⁶² TMOCA will be collected for comparison with TICS for potential use in future trials as it purports to assess executive function more than TICS. IQCODE will be collected from the relative/partner/carer by post or phone.

Health economics: EQ-5D-5L, EQ-VAS, return to work, hospitalisation, need for long term supportive care will be collected at 12 months.

Follow-up Brain MRI: all patients will have repeat brain MRI at 12 months to assess burden of WMH, microbleeds, lacunes, new infarcts or haemorrhage and atrophy and where feasible to assess diffusion tensor tissue parameters. These scans will be sent to Edinburgh for central blinded adjudication.

Follow-up at 6 and 12 months will be by post and telephone, blinded to allocated treatment. A trained assessor who is part of the central trial team and based either at the University of Edinburgh or University of Nottingham and who is blinded to treatment and baseline clinical information, will first confirm with the GP that the participant is contactable. They will then contact the patient or carer by post and phone to administer the questionnaires following a standardised script.

In addition to the assessments detailed above, participants will receive one to five informal contacts over the duration of their trial participation. One will consist of a participant newsletter and any other informal contacts will be a brief phone call or additional participant newsletter. During those contacts, a member of the central or site teams will update participants on the trial status, thank them for their continued help with the study, and give them an opportunity to ask questions.

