2. Per protocol: All consented participants with a primary outcome measure who received at least one dose of randomised medication and who had no protocol violation, e.g. they fulfilled all eligibility criteria.
3. Safety: All consented participants who received at least one dose of randomised medication.

Multiple variable analyses will include all patients with complete data for the dependent and each independent variable. All available data will be used, and missing data will not be imputed.

SECTION 5. TRIAL POPULATION**21 Screening data**

No screening logs will be kept so that data collection can be prioritised.

22 Eligibility

1. Clinical lacunar stroke syndrome.
2. Brain scanning with MR including diffusion imaging wherever possible, and obtained soon after the presentation with stroke, which showed either:
 - a. A recent, relevant (in time and location) acute small subcortical (i.e. lacunar) infarct on diffusion MR imaging.
 - b. If no visible acute small subcortical infarct on diffusion MR imaging then there is no competing pathology as a cause for stroke (e.g. no acute cortical infarct, no acute intra-cerebral haemorrhage, no stroke mimic such as tumour, subdural haematoma);
 - c. If only a CT brain scan is available, then there is a small relevant (in time and location) subcortical (i.e. acute lacunar) infarct, or if no infarct then there is no competing pathology as a cause for stroke (e.g. no acute cortical infarct, no acute intra-cerebral haemorrhage, no stroke mimic such as tumour, subdural haematoma).

3. Age >30 years.
4. Independent in activities of daily living (modified Rankin Scale <=2).
5. Capacity to give consent themselves.

23 Recruitment

Recruitment will be summarised in a CONSORT flow diagram.

24 Withdrawal/follow-up

Withdrawals, and missed follow-ups and their timing will be summarised in the CONSORT flow diagram.

25 Baseline patient characteristics

25a Baseline characteristics: These will comprise demographic, education, premorbid function, cognitive ability, medical history, blood pressure, stroke investigations, clinical and brain imaging parameters (Table 1).

25b Summarisation: Data will be shown as number (%), median [interquartile range] or mean (standard deviation) as appropriate.

SECTION 6. ANALYSIS

26 Outcome definitions

26a Specifications:

Primary endpoint

Feasibility of a Phase III efficacy trial assessed as:

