- Recruitment of sufficient patients, i.e. 400 patients in 24 months in the UK (and taking account of interruption due to COVID-19).
- >95% of randomised patients are retained for follow-up at one year.

Secondary outcomes - participant

Tolerability: 75% of patients will be able to tolerate trial medication, in at least half dose, up to one year after randomisation (i.e. less than 25% will stop trial medication completely through inability to tolerate the drugs).

Safety

- Symptoms of systemic or intracranial bleeding.
- The absolute risk of death, including fatal haemorrhage, does not differ significantly, i.e. fall outside the upper 95% CI of 2% per year on trial drugs versus no trial drugs, when given in addition to guideline stroke prevention drugs.
- There are no new ischaemic or haemorrhagic brain lesions or increase in SVD lesions on one year MRI significantly (at the p<0.01 level).

Efficacy

- Individual event-rates for stroke, TIA, myocardial ischaemia, cognitive impairment and dementia.
- The *combined rate* of recurrent stroke, MI, death, mild cognitive impairment (including dementia), dependency and new stroke lesions on scanning at 1 year will be 40-50% at one year after enrolment in order to allow detection of a modest but clinically-important reduction in poor outcomes in a phase III trial.
- Health economic measures include the health utility score (EQ-5D-5L) and the visual analogue score (EQVAS) at 12 months.

26b Units: Units will be shown in tables.

26c Calculations/transformations: Quality of life using UK weightings.

Brain frailty

Based on neuroimaging:

- Brain frailty = Atrophy + WML + Previous stroke lesion ⁷

- SVD score for CT = WML, lacunes; for MRI includes WMH, lacunes, PVS and microbleeds ¹⁵

Montreal cognitive assessment-modified (MoCA-m) trails

Since Trails A and B are performed, the MoCA trail is not collected but rather estimated from the Trails B score:

- If Trails B score <12 then MoCA trail = 0
- If Trails B score >=12 then MoCA trail = 1

27 Analysis methods

27a Methods

Primary endpoint

- Tabulation and graphical presentation of participant recruitment aiming for 400 participants in 24 months.
- Tabulation of retention of participants at one year aiming for >95%.

Analyses of secondary outcomes

Tabulations of:

- Tolerability to trial medications aiming for 75% of patients taking at least half dose for up to one year after randomisation.

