- Death, including fatal haemorrhage, aiming for less than outside the upper 95% CI of 2% per year.
- The *combined rate* of recurrent stroke, MI, death, cognitive impairment and dependency, aiming for 40-50% at one year after enrolment.

Comparison of rates of events between the treatment groups: cilostazol vs no cilostazol, ISMN vs no ISMN, and cilostazol and ISMN vs neither, for:

- Systemic or intracranial bleeding, recurrent cerebral and systemic vascular events, and vascular and non-vascular causes of death.
- Death, all cause.
- New ischaemic or haemorrhagic stroke lesion or increase in SVD lesions on MRI.
- Composite of: recurrent clinically-evident stroke, MI, death, cognitive impairment (including dementia) and dependency.
- Individual event: stroke (clinically-evident or imaging-detected ischaemic or haemorrhagic stroke to be reported separately), TIA, myocardial ischaemia, cognitive impairment and dementia.
- New infarcts and haemorrhages, absolute and change in WMH, microhaemorrhages, lacunes, atrophy imaging variables from central read of baseline imaging and one year MRI
- The comparisons of combined cilostazol and ISMN versus neither, whilst being very underpowered statistically, are presented since these may be the two groups studied in the planned follow-on trial.

Central tendency, comparisons and regressions will be analysed as follows (**Table D**).

Table D. Descriptive and analytical statistics

	Binary	Nominal	Ordinal	Continuous
Central tendency and distribution	N (%)	N (%)	Median [interquartile range]	Mean (standard deviation)
Comparisons	Chi-square (2x2)	Chi-square (2x2, or rxc)	Mann-Whitney U or Kruskal-Wallis	t-test (pooled) or 1-way ANOVA
Regression	Binary logistic regression (BLR)	-	Ordinal logistic regression (OLR)	Multiple linear regression (MLR)

27b Covariate adjustment: Analyses will be adjusted for minimisation covariates:

- Age, sex, stroke severity (NIHSS), dependency resulting from the stroke, systolic blood pressure, smoking status, time after stroke, years of education.

Covariate adjustment with continuous variables (age, NIHSS, SBP, time after stroke, years of education) will use original, not dichotomised, data.

27c Assumption checking: The assumption of proportionality will be tested using the likelihood test.

27d Alternative methods: If the data fail the assumption of proportionality (tested using the likelihood test), we will use alternative methods such as multiple logistic regression.

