Partially cavitated - FLAIR cavity but not=CSF	XX	XX (X)	XX (X)	XX (X)	BLR	XX	XX (X)	XX (X)	BLR	XX	XX (X)	XX (X)	BLR	XX
Partially cavitated - FLAIR=WMH T2=cavity	XX	XX (X)	XX (X)	XX (X)	BLR	XX	XX (X)	XX (X)	BLR	XX	XX (X)	XX (X)	BLR	XX
Partially cavitated - visible on T2 not FLAIR	XX	XX (X)	XX (X)	XX (X)	BLR	XX	XX (X)	XX (X)	BLR	XX	XX (X)	XX (X)	BLR	XX
Not cavitated (WML-like)	XX	XX (X)	XX (X)	XX (X)	BLR	XX	XX (X)	XX (X)	BLR	XX	XX (X)	XX (X)	BLR	XX
Disappeared	XX	XX (X)	XX (X)	XX (X)	BLR	XX	XX (X)	XX (X)	BLR	XX	XX (X)	XX (X)	BLR	XX
Become visible	XX	XX (X)	XX (X)	XX (X)	BLR	XX	XX (X)	XX (X)	BLR	XX	XX (X)	XX (X)	BLR	XX
Never visible	XX	XX (X)	XX (X)	XX (X)	BLR	XX	XX (X)	XX (X)	BLR	XX	XX (X)	XX (X)	BLR	XX
Evidence of new stroke (%)														

	N	All	OR/MD/ p- value			OR/MD/ p- value			ISMN + Cil		OR/MD/ p- value	
			ISMN	No ISMN	(95%CI)	Cil	No Cil	(95%CI)	None	(95%CI)		
Ischaemic	XX	XX (X)	XX (X)	XX (X)	BLR XX	XX (X)	XX (X)	BLR XX	XX (X)	XX (X)	BLR	XX
Haemorrhagic	XX	XX (X)	XX (X)	XX (X)	BLR XX	XX (X)	XX (X)	BLR XX	XX (X)	XX (X)	BLR	XX
Microhaemorrhages (%)	XX	XX (X)	XX (X)	XX (X)	BLR XX	XX (X)	XX (X)	BLR XX	XX (X)	XX (X)	BLR	XX
No. microhaemorrhages (%)					OLR XX			OLR XX			OLR	XX
1	XX	XX (X)	XX (X)	XX (X)		XX (X)	XX (X)				XX (X)	XX (X)
2	XX	XX (X)	XX (X)	XX (X)		XX (X)	XX (X)				XX (X)	XX (X)
3	XX	XX (X)	XX (X)	XX (X)		XX (X)	XX (X)				XX (X)	XX (X)
4	XX	XX (X)	XX (X)	XX (X)		XX (X)	XX (X)				XX (X)	XX (X)
>= 5	XX	XX (X)	XX (X)	XX (X)		XX (X)	XX (X)				XX (X)	XX (X)
Change from baseline	XX	XX [XX, XX]	XX [XX, XX]	XX [XX, XX]	OLR XX	XX [XX, XX]	XX [XX, XX]	OLR XX	XX [XX, XX]	XX [XX, XX]	OLR	XX
Small vessel disease score												
Total	XX	XX [XX, XX]	XX [XX, XX]	XX [XX, XX]	OLR XX	XX [XX, XX]	XX [XX, XX]	OLR XX	XX [XX, XX]	XX [XX, XX]	OLR	XX
Change from baseline	XX	XX [XX, XX]	XX [XX, XX]	XX [XX, XX]	OLR XX	XX [XX, XX]	XX [XX, XX]	OLR XX	XX [XX, XX]	XX [XX, XX]	OLR	XX
Atrophy												
Brain tissue volume reduction	XX	XX (X)	XX (X)	XX (X)	BLR XX	XX (X)	XX (X)	BLR XX	XX (X)	XX (X)	BLR	XX
Central brain tissue volume					OLR XX			OLR XX			OLR	XX
Modest	XX	XX (X)	XX (X)	XX (X)		XX (X)	XX (X)				XX (X)	XX (X)
Severe	XX	XX (X)	XX (X)	XX (X)		XX (X)	XX (X)				XX (X)	XX (X)
Cortical brain tissue volume					OLR XX			OLR XX			OLR	XX
Modest	XX	XX (X)	XX (X)	XX (X)		XX (X)	XX (X)				XX (X)	XX (X)
Severe	XX	XX (X)	XX (X)	XX (X)		XX (X)	XX (X)				XX (X)	XX (X)
Change from baseline					OLR XX			OLR XX			OLR	XX

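### Change in SVD score compares a two-item CT baseline with a four-item one-year MRI, which inflates apparent progression and costs precision

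*SAP*

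**What the plan says.** **Score.** SAP 26c gives one name to two scales: "SVD score for CT = WML, lacunes; for MRI includes WMH, lacunes, PVS and microbleeds". It does not state the points per item.

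**Baseline scan.** Protocol section 3: "Brain imaging with MRI is to be used in preference to CT for diagnosis of the index stroke wherever possible, but CT is allowed". Protocol 4.2 and SAP section 22 both admit patients on CT alone; the SAP wording begins "If only a CT brain scan is available, then there is a small relevant (in time and location) subcortical (i.e. acute lacunar) infarct". SAP Table 5 has a row for CT as the baseline scan type.

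**One-year scan.** Protocol 7.2: "all patients will have repeat brain MRI at 12 months to assess burden of WMH, microbleeds, lacunes, new infarcts or haemorrhage and atrophy".

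**Analysis.** SAP Table 9 has a block headed "Small vessel disease score" with a row for the total and a row for change from baseline. Both are analysed by ordinal logistic regression in all three comparisons. For the individual imaging variables, SAP 27a plans "absolute and change in WMH, microhaemorrhages, lacunes, atrophy imaging variables from central read of baseline imaging and one year MRI", with no limit by modality.

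**Adjustment and missing data.** SAP 27b: "Analyses will be adjusted for minimisation covariates". The list that follows contains neither baseline scan type nor baseline SVD score. SAP section 20 keeps patients with complete data for the variables in the model and does not impute.

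**Use of the result.** The safety outcomes in SAP 26a include an absence of significant increase in SVD lesions on the one-year MRI, at p<0.01.

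**The concern.** A change score means something only if both ends are measured on the same scale. For a CT-baseline patient the score can reach two items at entry and four at one year. The extra items, perivascular spaces (PVS) and microbleeds, may have been present throughout and are simply counted for the first time.

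The complete-case rule does not remove these patients. A CT score is defined, so their baseline score is not missing. SAP section 28 prefers the approach that makes greatest use of the available data, which points towards including them.

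Two things are at stake. The reported absolute progression in SVD score would be too high, which matters in a trial meant to inform a later one. The extra noise also makes a real arm difference harder to detect. Because the safety statement treats the absence of a significant increase as reassurance, lost precision on this row works towards reassurance.

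**Working it through.** The documents give no expected change, sample size or power for the SVD score, so there is no figure of the plan's own to reproduce.

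**Inputs from the documents**
- Two items on CT, four on MRI (SAP 26c).
- 363 recruited (SAP Table 2), and at least 15% expected to miss the repeat MRI (Protocol 9.1): 363 × 0.85 = 308.6, taken as n = 308, or 154 per arm in a 1:1 comparison.
- Two-sided 5% level (SAP section 16).

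**Assumed inputs**
- CT-baseline share c: 10% to 50%.
- Prevalence of a PVS point, p: 20% to 60%; of a microbleed point, b: 10% to 30%; the two independent.
- One point per item.
- True one-point progression q = 25%, so true variance s = 0.25 × 0.75 = 0.1875.

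Observed change in a CT-baseline patient is the true change plus any PVS point and any microbleed point already present.

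**False rise among CT-baseline patients**
- Mean = p + b: 0.2 + 0.1 = 0.3, to 0.6 + 0.3 = 0.9 points.
- Share with a rise of at least 1 and no true change = 1 − (1 − p)(1 − b): 1 − 0.8 × 0.9 = 28%, to 1 − 0.4 × 0.7 = 72%.

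**False mean rise in the whole cohort** = c(p + b): 0.1 × 0.3 = 0.03, to 0.5 × 0.9 = 0.45 points.

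**Variance of the change** = s + c[p(1 − p) + b(1 − b)] + c(1 − c)(p + b)²

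| Case | c | p | b | Total variance | Ratio to 0.1875 |
|---|---|---|---|---|---|
| Low | 0.1 | 0.2 | 0.1 | 0.1875 + 0.0250 + 0.0081 = 0.2206 | 1.18 |
| Central | 0.2 | 0.4 | 0.2 | 0.1875 + 0.0800 + 0.0576 = 0.3251 | 1.73 |
| High | 0.5 | 0.6 | 0.3 | 0.1875 + 0.2250 + 0.2025 = 0.6150 | 3.28 |

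Adjusting the four-item change for baseline modality removes only the last term. The ratio is then (0.1875 + 0.0250)/0.1875 = 1.13 in the low case and (0.1875 + 0.2250)/0.1875 = 2.20 in the high case, so a covariate alone does not cure the problem.

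**Power illustration.** True progression 30% v 20%, p = 0.4, b = 0.2, 154 per arm. Power = Φ(0.10/√(2 × variance/n per arm) − 1.96). With no artefact: 0.10/√(2 × 0.1875/154) = 2.03, giving 53%.

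| CT share | As planned | MRI-MRI pairs only |
|---|---|---|
| 10% | 41% | 49% |
| 20% | 34% | 44% |
| 30% | 29% | 40% |
| 50% | 25% | 30% |

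Restriction does not always win. With p = 0.2, b = 0.1 and c = 50%, the planned analysis has 33% power and MRI-MRI pairs 30%.

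**Validity of the comparison.** Baseline modality is fixed before allocation, so the artefact has the same expected size in both arms. A simulation of 4,000 trials per CT share, using the Mann-Whitney test in place of unadjusted ordinal regression, gave type I error of 4.6% to 5.0%. For 30% v 15% true progression, power fell from about 89% to 81%, 71%, 65% and 50% at CT shares of 10%, 20%, 30% and 50%.

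**The case against.** The strongest reply is that this concerns one row pair in one table. The total SVD score is not named among the outcomes in SAP 26a or in the imaging list of 27a. The safety statement on lesions also rests on item-level rows of Table 9: new ischaemic and haemorrhagic stroke, number of lacunes, Fazekas scores and regional white matter change. None of these mixes a two-item with a four-item scale. Every size given above is assumed; at the low end the cohort-wide false rise is 0.03 points. All of this stands, and it limits the importance of the point without removing the mismatch.

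A reader might infer three stronger things that the documents do not support:

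- **That the treatment comparison is biased.** It is not, in expectation. Modality is not a minimisation factor, so CT share may differ between arms by chance, but that is random error. It is largest in the dual-versus-neither comparison, which SAP 27a already describes as very underpowered.
- **That change in microhaemorrhage number is corrupted in the same way for all patients.** The CT score has no microbleed item, and SAP section 20 keeps only patients with complete data. The natural reading is that a CT baseline is missing for that row, and nothing codes it as zero.
- **That change in SVD score is a named efficacy outcome or drives the phase III sample size.** The only imaging element under efficacy in 26a is new stroke lesions, and the sizing in Protocol 9.1 and SAP section 11 does not use this score.

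It can also be said that the SAP never writes out the subtraction for CT-baseline patients. That is true. It follows from the two definitions, the permitted CT baseline, the MRI follow-up and an unrestricted change row. If MRI pairs are intended, the SAP does not say so.

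**Conclusion.** The point holds for the SVD score change row of Table 9. Followed as written, the plan subtracts a two-item score from a four-item score in CT-baseline patients and counts pre-existing PVS and microbleeds as progression, by up to 2 points if each item scores one. The harm is inflated absolute progression and lost precision on a secondary row that supports the p<0.01 safety statement; it is not a biased arm comparison.

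The mismatch is certain from the text, but its size is not. The ranges rest on the assumed CT share, prevalences, independence, points per item and true progression listed above. Any difference between CT and MRI in detecting white matter lesions or lacunes was not modelled. The power figures use the 5% level; at the 1% level of the safety statement they would all be lower. The point deserves correction before database lock but does not touch the primary endpoint.

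**What to change.** In SAP 26c and Table 9:

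1. Restrict change in the four-item SVD score to patients with MRI at both times.
2. For all patients, analyse change on the two shared items (white matter lesions or hyperintensities, and lacunes), with baseline modality as a covariate because CT and MRI may also detect these differently.
3. Report the number of CT-baseline patients by arm beside these rows.
4. As a clarification, state that microhaemorrhage change uses MRI-MRI pairs only and that a CT baseline counts as missing, not zero.
5. State the points per item in 26c.

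This is SAP wording and needs no new data. The cost is fewer patients in the four-item change analysis. At a high CT share with low PVS and microbleed prevalence this can lose a little precision (30% v 33% power in the case shown above). Elsewhere in the range examined, the restricted analysis is the more precise one as well as the interpretable one.
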